#### *Data and Safety Monitoring*

Subjects will be informed that if they experience any adverse events with the use of episil®, that they should discontinue the use of the product immediately. Depending on the severity of the adverse event the patient will be advised to either call 911 or [name] to report the event. An Unanticipated Problems Tracking Log Form will be used to report adverse events to report them to CPHS. Any adverse event will then be immediately reported to Camurus AB, the manufacturer of episil®.

An Unanticipated Problems Tracking Log Form will be used to record and report any adverse events that are unexpected, related and put the subjects or others at harm, meet the definition of Unanticipated Problems Involving Risks to Subjects or Others and will be reported to the Committee for the Protection of Human Subjects.

#### *Surgical Procedures & Postoperative Care*

As stated above, periodontal residents under the direct supervision of periodontal faculty will perform the FGG procedure in all subjects. The FGG procedure will be performed following the surgical technique of Sullivan and Atkins or Miller. The donor tissue for the FGG procedure will be retrieved from either the right or left side of the palate. The FGG donor sites will be of a standardized size of 10 mm x 10 mm. As stated above, subjects in the control group will receive a hemostatic gauze, Surgicel®, covered by a cyanoacrylate dressing, PeriAcryl®90, at the donor site while the subjects in the test group will receive the same brand of hemostatic gauze, Surgicel®, but covered with episil®. Subjects in the test group will be given the remainder of the bottle of episil® with instructions for home application up to 3 times daily. Postoperative instructions will include discontinuing tooth brushing and flossing around the surgical site for the first 3 post-operative weeks. Subjects will be provided with a prescription for ibuprofen (600 mg) to take as needed for analgesia, unless contraindicated. Acetaminophen with 30mg of codeine will be prescribed to subjects unable to ingest ibuprofen.

The LDF measurements in the FGG donor site and on the contralateral side of the palate will be recorded in four sites. A clear acrylic stent will be fabricated for each subject from individual subjects' dental casts. Holes will be made in the stent in four locations on each the right and left sides of the palate. One site located centrally, one close to the mesial, one close to the distal and one close to the apical of the FGG donor site and in the same locations on the contralateral side of the palate will be measured at each of the specified postoperative appointments. The LDF measurement will be performed at baseline prior to surgery, immediately after harvesting of the FGG donor site, and on post-operative days 3, 7, 14 and 21. The LDF measurements will be performed with the tip of the fibre optic probe inserted into the holes of the individual acrylic stent. The LDF probe will be placed at a

standardized location perpendicularly to the tissues and at a distance of 0.5 mm from the tissues and will remain motionless during the LDF measurements.

Below is a summary of the timeline of the study:

**First clinic visit (Screening visit):** Discussion of study and attain informed consult for participation in the study; medical history will be updated, vital signs will be taken, and an upper arch alginate impression will be taken in order to create a plastic stent, which will be worn during the laser Doppler flow measurements.

**Second clinic visit (Day of Surgery):** The day of surgery, the laser Doppler flowmetry readings will be performed before the surgery and then again immediately after harvesting of the FGG donor site. Subjects will receive 4 copies of the Visual Analog Scale Form/Questionnaire to be completed at their homes on days 1, 2, 5, and 10 postoperatively, which will be labeled accordingly. Subjects assigned to the test group will receive a manual-metering pump containing sufficient episil® for the duration of the study. Subjects in the test group will be instructed to use the pump up to 3 times a day. Instructions for home application of the episil® will be given orally and in writing at this appointment.

**Day 1 post-operative:** All subjects will complete at home the Day 1 Post-Operative Visual Analog Scale Form/Questionnaire.

**Day 2 post-operative:** All subjects will complete at home the Day 2 Post-Operative Visual Analog Scale Form/Questionnaire.

**Day 3 post-operative (3rd clinic visit):** All subjects will bring the 2 completed Visual Analog Scale Forms/Questionnaires to the day 3 post-operative clinic appointment and will complete the Day 3 Post-Operative Visual Analog Scale Form/Questionnaire during this appointment. The laser Doppler flowmetry readings will be performed on the free gingival graft donor site and on the contralateral side of the palate utilizing the fabricated stent with holes for the Doppler probe positioning for repeatability of readings. 3% H2O2 will be applied to the FGG donor site with a syringe and the appearance of bubbles will be recorded as a dichotomous variable.

**Day 5 post-operative:** All subjects will complete at home the Day 5 Post-Operative Visual Analog Scale Form/Questionnaire.

**Day 7 post-operative (4th clinic visit):** All subjects will bring completed Visual Analog Scale Form/Questionnaire to the day 7 post-operative appointment and will complete a Day 7 Post-Operative Visual Analog Scale Form/Questionnaire during that appointment and laser Doppler flowmetry readings will be performed on the free gingival graft donor site and on the contralateral side of the palate. 3% H2O2 will be applied to the FGG donor site with a syringe and the appearance of bubbles will be recorded as a dichotomous variable.

**Day 10 post-operative:** All subjects will complete at home the Day 10 Post-Operative Visual Analog Scale Form/Questionnaire.

**Day 14 post-operative (5th clinic visit):** All subjects will bring completed Visual Analog Scale Form/Questionnaire to the day 14 post-operative appointment and will complete a Day 14 Post-Operative Visual Analog Scale Form/Questionnaire and laser Doppler flowmetry readings will be performed on the free gingival graft

donor site and on the contralateral side of the palate. 3% H2O2 will be applied to the FGG donor site with a syringe and the appearance of bubbles will be recorded as a dichotomous variable.

**Day 21 post-operative (6th clinic visit):** All subjects will attend the day 21 post-operative appointment and will complete a Day 21 Post-Operative Visual Analog Scale Form/Questionnaire and laser Doppler flowmetry readings will be performed on the free gingival graft donor site and on the contralateral side of the palate. 3% H2O2 will be applied to the FGG donor site with a syringe and the appearance of bubbles will be recorded as a dichotomous variable.

Below is a chart of the timeline of the study:

| Procedure  | Visit
1
Screening | Visit
2
Day of
Surgery | Visit
3
3 Day
Post-op | Visit
4
7 Day
Post-op | Visit
5
14 Day
Post-op | Visit
6
21 Day
Post-op |
|--|-------------------------|---------------------------------|--------------------------------|--------------------------------|---------------------------------|---------------------------------|
| Medical History                                     | ✓                       | ✓                               | ✓                              | ✓                              | ✓                               | ✓                               |
| Vital Signs   | ✓                       | ✓                               | ✓                              | ✓                              | ✓                               | ✓                               |
| Complete Visual
Analog Scale/
Questionnaire |                         |                                 | ✓                              | ✓                              | ✓                               | ✓                               |
| Doppler Flowmetry
(FGG donor site)              |                         | ✓                               | ✓                              | ✓                              | ✓                               | ✓                               |
| Doppler Flowmetry
(Contralateral side)          |                         | ✓                               | ✓                              | ✓                              | ✓                               | ✓                               |
| 3% H2O2
(FGG donor site)  |                         |                                 | ✓                              | ✓                              | ✓                               | ✓                               |

#### *Statistical Analysis*

Descriptive statistics will be expressed as means+/- SD and frequency distributions. Intergroup (FFG donor site using episil® and Surgicel® (test) and FGG donor site with PeriAcryl®90 and Surgicel® (control)) comparisons at 1, 2, 3, 5, 7, 10, 14 and 21 days will be analyzed by the Mann-Whitney U test. The Wilcoxon signed-rank test will be used for intragroup comparisons between 1, 2, 3, 5, 7, 10, 14 and 21 days. Differences in frequency distributions between the episil® group and the PeriAcryl®90 group will be analyzed by the Fisher exact test. Associations

between pain VAS scores and the number of analgesic pills or number of days analgesics were taken will be examined by the Pearson correlation coefficient. The significance level for rejection of the null hypothesis will be set at  $\alpha = 0.05$ .

All LDF recordings, which may be impaired by artifacts caused by the relative motion of the probe, will be excluded. An average of the 2-minute period of each individual recording will be calculated. Changes of blood flux values in the FGG donor site will be expressed as the difference ( $\Delta PU$ ) between the PU value at a specific site at a specific observation time point ( $PU_t$ ) and the individual baseline value of the same site ( $PU_0$ ):  $\Delta PU_t - PU_0$ .

Descriptive statistics will be performed using the SPSS statistical software. The  $\Delta PU$  values in the FGG donor site will be analyzed using the general linear model (GLM) univariate test, after verification of the assumptions of homogeneity of variance and normality of the residual distribution. The observation time and point and the position (mesial, center, distal and apical to the FGG donor site) will be modeled as fixed factors and the patient as a random factor with the  $\Delta PU$  as the dependent variable. The Dunnett two-sided *t*-test will be used, in order to evaluate the differences between baseline and subsequent time points and between different positions in the FGG donor site during the overall observational period. Data will be presented as mean SE. Statistical significance will be accepted at  $p < 0.05$ .

The outcome analysis of the time needed to obtain complete re-epithelialization of the FGG donor site will be made by comparing experimental groups on the frequency distribution of patients experiencing complete re-epithelialization in each of the 4 post-operative visits. The Williams-adjusted log-likelihood ratio was performed, followed by *post-hoc* tests using Bonferroni-corrected Fisher's exact test (2-tailed).

Based on a sample size of  $n = 40$  (20 per group), a repeated measures analysis will have 80% power to detect an effect size of  $f = .57$ . For a sample size of  $n = 30$  (15 per group), the same analysis will have 80% power to detect an effect size of  $f = .67$ , while a sample size of  $n = 20$  (10 per group) will have 80% power to detect an effect size of  $f = .83$ . All of these effect sizes are classified as large effects by Cohen's guidelines (1988), or large differences in the change in pain score between the two groups.

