instructions for self-application as needed 3 times daily for pain relief. A sufficient supply of the episil® will be provided to the test subjects for the study duration. The total duration of the study per subject will be 21 days from the day of the surgical procedure. The primary outcome of postoperative pain will be determined by the subjects recording their postoperative pain threshold using a Visual Analog Scale Form/Questionnaire and the number of analgesic pills taken each day at 1, 2, 3, 5, 7, 10, 14 and 21 days postoperatively. The Visual Analog Scale Form/Questionnaire for post-operative days 1, 2, 5 and 10 will be completed at the subject's place of residence, while the Visual Analog Scale Form/Questionnaire for days 3, 7, 14 and 21 will be completed at the subject's post-operative appointments at the dental clinic. The Visual Analog Scale Form/Questionnaire will evaluate the subjects' postoperative pain using a visual analog scale (VAS) scores from 1 to 10, with 1 indicating minimal pain and 10 indicating severe pain. If no pain is present, a score of 0 will be given. The levels of postoperative pain will be classified as none to minimum if the score is "0 to 3," moderate for "4 to 6," and severe for "7 to 10." None to minimal pain will mean little or no discomfort; moderate is any pain that bothers the subject and mildly affects normal function; and severe will be considered any pain that will not be tolerated and may even disrupt the subject's daily functions.

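### The plan does not say which pain measure, day or test decides the primary hypothesis, and its power statement is for a repeated measures analysis that the pain analysis does not contain

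*Combined protocol and SAP*

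**What the plan says.** Study Population and Design sets the primary outcome: "The primary outcome of postoperative pain will be determined by the subjects recording their postoperative pain threshold using a Visual Analog Scale Form/Questionnaire". Pill use belongs to the same definition, which goes on to list a second record: "and the number of analgesic pills taken each day at 1, 2, 3, 5, 7, 10, 14 and 21 days postoperatively". That is two measures on eight days. The same section also bands the VAS score: "The levels of postoperative pain will be classified as none to minimum if the score is" 0 to 3, with further bands at 4 to 6 and 7 to 10.

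Statistical Analysis then plans, for the two arms, that "comparisons at 1, 2, 3, 5, 7, 10, 14 and 21 days will be analyzed by the Mann-Whitney U test". The sentence does not name the variable. Two further sentences follow: "The Wilcoxon signed-rank test will be used for intragroup comparisons between 1, 2, 3, 5, 7, 10, 14 and 21 days", and "Differences in frequency distributions between the episil® group and the PeriAcryl®90 group will be analyzed by the Fisher exact test", the latter without naming a variable or a day. "The significance level for rejection of the null hypothesis will be set at" 0.05. Nothing ranks one of these results above the others.

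The only correction for comparing arms concerns re-epithelialization, a secondary outcome: the words "tests using Bonferroni-corrected Fisher" occur there and have no counterpart for pain. The Dunnett test in the blood-flow analysis compares time points and positions, not arms.

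The section closes with the sample size. It attributes 80% power to a repeated measures analysis at f = .57, .67 and .83 for 40, 30 and 20 subjects, and describes these as large between-group differences in how the pain score changes. It states neither the tested effect (arm, or arm by day) nor the number of time points.

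**The concern.** Background, Aim, & Hypothesis predicts that patient-based outcomes will be better with episil. The plan does not say which result would confirm or refute this. It is silent on what to conclude if the arms differ on day 2 but not on day 7, or if VAS scores are lower while pill counts are higher. The deciding result could therefore be chosen after the data are seen.

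The power statement does not settle the matter, because it describes an analysis that is not planned for pain. A reader can neither treat that analysis as the primary test nor apply its 80% to the daily tests that are planned.

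**Working it through.** **1. Planned against powered analysis.**

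| | Pain analysis as planned | Sample-size paragraph |
|---|---|---|
| Method | Mann-Whitney on each day | Repeated measures analysis |
| Quantity | Difference between arms on a day | Between-group difference in the change in pain score |
| Time points | 1, 2, 3, 5, 7, 10, 14, 21 (eight) | Not stated |
| Tested effect | Arm, day by day | Not stated |

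The only linear model in the section is for blood flow. Its factors are time, position and patient, with no treatment arm, so it cannot be the missing pain analysis.

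**2. The stated power.** Take an arm-by-time F test with m time points, df1 = m - 1, df2 = (m - 1)(N - 2), noncentrality f²N and alpha 0.05. The noncentralities at the stated values are 0.57² × 40 = 13.0, 0.67² × 30 = 13.5 and 0.83² × 20 = 13.8.

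| Design | f for 80% power at N = 40 / 30 / 20 | Power at stated f |
|---|---|---|
| m = 6, no sphericity correction | 0.575 / 0.667 / 0.826 | 79.3 / 80.4 / 80.5% |
| m = 4, epsilon 0.8 (df and noncentrality × 0.8) | 0.575 / 0.668 / 0.830 | about 80% |
| m = 8 (the pain days), no correction | 0.607 / 0.704 / 0.871 | 73.8 / 75.1 / 75.3% |

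The first two rows both reproduce the stated figures, so the design behind them cannot be identified. A plain two-group test does not reproduce them: it gives about 94% power at the stated f.

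**3. False positives if any significant VAS day counted.** The 20 per arm comes from the plan. Two-sided tests are assumed, because sidedness is not stated for pain. The between-day correlation is also assumed. If the eight days were independent, the risk would be 1 - 0.95⁸ = 1 - 0.663 = 0.337. Simulation of eight Mann-Whitney tests with no true difference and an equal correlation between all days gave:

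| Correlation | 0.3 | 0.5 | 0.7 | 0.9 |
|---|---|---|---|---|
| Any day, either direction (continuous scores) | 30.2% | 25.5% | 19.9% | 12.7% |
| Any day, favouring one named arm (continuous scores) | 15.2% | 12.7% | 10.0% | 6.4% |
| Any day, either direction (integer 0-10 scores with ties) | 29.8% | 25.1% | 19.7% | 13.4% |

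With integer scores, the risk favouring episil ran from 6.5% to 15.8% over the correlation patterns tried. A single day's test held 4.3-5.1%. Holm over the eight days held 2.0-4.0%.

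**4. Cost of adjustment.** The first Holm step is 0.05/8 = 0.00625. With 20 per arm, 80% power, normal data and a Mann-Whitney efficiency of 3/π = 0.955, the detectable difference on one day rises from about 0.93 SD at 0.05 to about 1.22 SD at 0.00625.

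**5. Why the tested effect must be stated.** In simulations with assumed pain means and SD 2.2, a 2-point benefit on days 1-3 gave 23-52% power for the arm effect over eight days and 82-100% for arm by day. A 1.5-point benefit on all days gave 57-95% and 11-36%. These figures show only that the choice matters. They do not favour either effect.

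**The case against.** The strongest reply is that the plan never says any significant day would count. That is right: 13-30% is not the type I error rate of this plan, and a reader who infers so goes beyond the text. The hypothesis is also directional, so 6-16% is the nearer figure for falsely supporting it. What remains is that no rule is given, so the any-day reading is not excluded either.

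A second reply is that the plan does name a test for comparing arms, and that VAS looks like the leading measure: the power paragraph speaks of pain score, and pill counts are named in the analysis only for correlation with VAS. This is fair. The fault is that measures, days and tests are not ranked, not that no test exists. But the definition of the primary outcome lists pill count beside VAS, so the lead is only implied.

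Three further inferences are tempting and not supported:
- *The power was computed for blood flow, which has six time points.* Four points with a sphericity correction fit as well, and VAS is completed at four clinic visits.
- *The Fisher tests add eight more tests of VAS classes.* The sentence names neither variable nor day, and the plan uses similar wording for re-epithelialization.
- *The change in pain score is undefined because no pre-surgery VAS exists.* It can mean different courses over time, which needs no pre-surgery value.

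**Conclusion.** The point holds on the text. The primary outcome has two measures on eight days, no deciding comparison and no multiplicity rule, and the stated power is for an analysis that is not planned for pain. Neither part depends on simulation.

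The size of the false-positive risk is conditional. It is about 13-30% in either direction and about 6-16% favouring episil, if any significant VAS day counted, with 20 per arm and an assumed between-day correlation of 0.9 to 0.3. The 74-75% power with eight pain days is an illustration under one F-test convention. It does not show that the trial is underpowered, because the intended test is unknown.

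**What to change.** Before data are seen, name VAS as the primary measure and prespecify one between-arm test at two-sided 0.05. The preferred choice is the repeated measures analysis that the sample-size paragraph already refers to, applied to the VAS days, with its tested effect (arm, or arm by day) and time points stated. If primary claims about individual days are wanted instead, keep the eight VAS Mann-Whitney tests with Holm adjustment.

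Make the remaining daily tests, the pill counts and any Fisher tests secondary, and the within-arm Wilcoxon tests descriptive. Restate the sample-size paragraph so that its detectable effect is for the chosen test and number of time points. For example, an uncorrected arm-by-day F test on eight days, under the convention used above, needs f of about .61, .70 and .87 at 40, 30 and 20 subjects.

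The cost is wording and one recalculated power sentence. Visits, data and sample size are unchanged. With a single test, day-specific claims become secondary. With Holm, the detectable difference on a day is larger at the first step, as calculated above.

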Oral mucositis in advanced stages, similar to a FGG donor site, can be extremely painful, preventing a patient from eating and even disrupting the patient's daily functions. The aim of this study will be to compare patient-based outcomes, specifically postoperative pain, at the FGG donor sites, using an interventional parallel-group design, whereby a hemostatic gauze, Surgicel®, will be placed within all of the palatal donor sites and covered with either episil® (test) or a cyanoacrylate dressing, PeriAcryl®90 (control). The secondary aim of this study will be to compare gingival healing via measurement of the gingival blood flow at the FGG donor sites by the laser Doppler flowmetry (LDF) technique, by monitoring blood perfusion. The hypothesis for the present study is that patient-based outcomes and gingival blood flow will be more favorable for the FGG donor sites being covered by the test wound dressing material episil® compared to the control dressing.

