#### *Study Population and Design*

Forty subjects will be recruited from the Periodontics and Dental Hygiene Clinic and the UTDentists Practice, located at the UTHealth School of Dentistry in Houston, Texas, where the study will be performed. Only subjects who have already formally agreed to receive a FGG as part of their overall periodontal treatment plan will be recruited. Inclusion criteria will be 18 years of age or older, patient of record at UTHealth School of Dentistry Houston Texas, signed treatment plan for a FGG, and the ability to provide research informed consent. Exclusion criteria will be any allergies to any of the ingredients in episil® including allergies to peanuts, soy or peppermint oil, smokers, pregnant or breast feeding women, and inability or unwillingness to provide informed consent. As stated above, elective surgical procedures are not routinely performed on pregnant or lactating women and are postponed until after childbirth and or completion of lactation. Exit criteria will be unwillingness or inability to continue in the study and non-compliance with study procedures and appointments. The Institutional Review Board of The University of Texas will approve the study protocol, questionnaires and informed consent form.

The study will be of an interventional parallel-group design. A computer generated randomization scheme will assign the subjects to one of the two treatment groups. All subjects will have the gingival grafting procedure, the free gingival graft, performed at sites lacking attached keratinized gingival tissues. The palatal donor site in subjects assigned to the control group will receive the hemostatic agent, Surgicel®, covered by the cyanoacrylate dressing, PeriAcryl®90. The palatal donor site in the subjects assigned to the test group will receive the hemostatic agent, Surgicel®, covered by episil®. Additionally, the subjects in the test group will be given the remainder of the bottle of episil® to take home with

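### Change in pain over time is tested only within each arm, without correction; no between-arm test of change is planned

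*Combined protocol and SAP*

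**What the plan says.** The Background, Aim, & Hypothesis section sets a comparison between dressings: "The aim of this study will be to compare patient-based outcomes, specifically postoperative pain, at the FGG donor sites". Subjects are randomized ("A computer generated randomization scheme will assign the subjects to one of the two treatment groups"), and pain is recorded as a VAS score together with "the number of analgesic pills taken each day at 1, 2, 3, 5, 7, 10, 14 and 21 days postoperatively". The study timeline shows no VAS score before surgery.

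The Statistical Analysis section plans two kinds of test on these scores. Between arms, each of the eight days "will be analyzed by the Mann-Whitney U test". Within arms, "The Wilcoxon signed-rank test will be used for intragroup comparisons between 1, 2, 3, 5, 7, 10, 14 and 21 days". Then: "The significance level for rejection of the null hypothesis will be set at" 0.05. No adjustment is stated for pain.

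Other outcomes are treated differently. Re-epithelialization gets post-hoc "tests using Bonferroni-corrected" Fisher tests, and for blood flow a Dunnett test is used "in order to evaluate the differences between baseline and subsequent time points and between different positions in the FGG donor site".

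The power paragraph at the end of the same section refers to a repeated measures analysis and describes its effect sizes as differences between the groups in how pain changes. No such analysis appears among the planned pain tests.

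**The concern.** A signed-rank test within one arm asks whether pain differed between two days in that arm. It contains no contrast between dressings. The Background already cites a significant difference between 3-day and 3-week pain at these donor sites, so the tests will largely confirm that wounds heal.

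The plan offers nothing else on change. The Mann-Whitney tests compare levels one day at a time. A reader who wants to know whether pain fell faster with one dressing, which is the quantity the power statement describes, would have only two separate lists of within-arm p-values to set side by side. A day pair significant in one list and not in the other is easily read as faster relief. It is not evidence of that, because such disagreement is common when the dressings are identical.

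**Working it through.** **The plan's own figure.** The documents give no count of within-arm tests and no familywise error. The nearest figure is the power statement: 80% at f = .57, .67 and .83 for n = 40, 30 and 20. With λ = f²N, λ is .57² × 40 = 13.0, .67² × 30 = 13.5 and .83² × 20 = 13.8. A plain two-group F test at 0.05 then has power of 94.0%, 94.3% and 93.9%. The number of repeated measures, their correlation and the term tested are not stated, so the 80% is neither confirmed nor refuted. Nothing below depends on it. What matters is the analysis it names.

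**Count of tests.** There are eight days and two arms.
- All pairs: 8 × 7 / 2 = 28 per arm, and 2 × 28 = 56.
- Adjacent days, or each later day against day 1: 7 per arm, and 2 × 7 = 14.

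If every null were true and the tests independent, the chance of at least one false positive would be 1 − 0.95^56 = 94.3%, or 1 − 0.95^14 = 51.2%. These are not realistic error rates here: if pain falls, most of the nulls are false.

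**One comparison, identical arms.** If each arm reaches significance with probability p, the chance that exactly one arm does is 2p(1 − p):

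| p | 2p(1 − p) |
|---|---|
| 0.05 | 0.095 |
| 0.20 | 0.32 |
| 0.50 | 0.50 |
| 0.80 | 0.32 |
| 0.95 | 0.095 |

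Disagreement is most frequent when the fall between two days is moderate for 20 subjects.

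**All comparisons together, by simulation.** Both arms have the same true course, 20 subjects per arm, integer scores limited to 0–10, AR(1) correlation across the eight assessments, and two-sided signed-rank tests at 0.05. The documents give no VAS SD, correlation or pain course, so all of these are assumptions. Sidedness is also not stated in the plan. Entries are the percentage of trials with at least one comparison significant in one arm only.

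| Assumed course, days 1 to 21 | SD; correlation; trials per setting | All pairs | Adjacent days | Versus day 1 |
|---|---|---|---|---|
| 5, 5, 4.5, 4, 3, 2, 1, 0.3 | 2.5; 0.7; 400 | 99.75% (mean 6.0 of 28 pairs) | 98% | 75% |
| Same | 2.5; 0.5; 400 | 100% (mean 6.3) | 94% | 75% |
| Three declining courses | 2 or 2.5; 0.7 or 0.5; 150 | 98–100% (mean 4.2–8.7) | 86–97% | 55–85% |
| Three declining courses | 1.5 or 2.5; 0.5 or 0.7; 200 | 96–100% | not run | 32–85% |
| Further declining courses | other assumed values | 97–100% | not run | 17–72% |
| Flat at 5 | 2.5; 0.7; 400 | 74.5% (mean 2.8) | 48% | 37.5% |

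The range against day 1 is wide for the reason the first table shows. Where pain falls steeply relative to its SD, p is close to 1 in both arms and they agree. The ranges cover the settings tried and are not bounds: a steeper fall with little variability would give lower values.

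**The case against.** The strongest reply has four parts.

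- **The dressings are compared directly.** The sentence before the within-arm tests assigns that comparison to the Mann-Whitney test on each of the eight days. This is correct. A reader might infer that the plan does not compare pain between arms at all, and the documents contradict that. What is missing is narrower: a between-arm test of change.
- **No misuse is planned.** A reader might also infer that the trial intends to claim benefit from within-arm significance. Nothing in the Statistical Analysis section says so. But nothing labels these tests descriptive either, and they are the only planned pain tests of change over time.
- **All 56 tests may not be intended.** The sentence does not say every pair. Eight listed days with no reference day make that reading natural, but 14 tests is possible. A statement that pain fell by a given day compares that day with an early one, so the versus-day-1 column is the relevant one. There, a disagreement favouring one arm named in advance occurred in about 8–43% of the simulated trials with declining pain. This stands: the size depends heavily on the reading.
- **Multiplicity is secondary.** If pain falls, most within-arm nulls are false, and a correction would not turn these tests into comparisons of dressings. This also stands. The missing correction is worth recording, but the main defect is the absent arm contrast.

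**Conclusion.** The point holds in limited form. The plan has up to 56 uncorrected within-arm tests on the primary outcome (14 on the narrower readings), and none compares the dressings. With identical arms and a shared declining course, at least one comparison very likely reaches significance in one arm only under all pairs (96–100% of trials in the settings tried). Against day 1 the chance is anywhere from modest to high (17–85%). If pain stayed flat, the all-pairs figure would be about 75%, though the Background makes a flat course implausible. Every percentage rests on assumed SDs, correlations and courses.

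The more consequential half needs no simulation. The power statement describes a between-arm difference in change from a repeated measures analysis, and the planned pain analyses contain no test of that quantity. The plan should be revised on this point, but it does not lack a between-arm comparison of pain levels.

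**What to change.** In the Statistical Analysis section:

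1. Delete the within-arm signed-rank tests, or label them descriptive and state that no inference about the dressings will be drawn from them. If they stay, say which days are compared.
2. Show the pain course by median and IQR for each day and arm.
3. Prespecify one between-arm analysis of change over time: either an arm-by-day term in a repeated measures model, or a single between-arm comparison of each subject's early-to-later change (for example, the average of days 1–3 to day 7). Fix the days before any outcome data are seen.
4. Restate the power paragraph for the analysis chosen, with the number of assessments, the assumed correlation and the term tested.

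This costs SAP wording and a repeat of the power calculation; no new data are needed. The within-arm p-values are lost or demoted, and they answer no stated aim. One limit should be stated: with no score before surgery, change has to be measured from a day on which the dressing is already in place. An effect present by day 1 would show in the between-arm comparison of levels rather than in the change, so the two should be reported together, with the plan saying which one carries the conclusion.
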